1 GENERAL

1.1 Introduction

The Aer-O-Scope® Colonoscope System is a joystick operated self-propelled, disposable colonoscope designed to improve visualization behind folds, eliminate the possibility of disease transmission and be safe and easy to use. The Aer-O-Scope has a unique omni-directional 360° view optics, that provide the operator with a 360° field of view.

There is no perfect gold standard for colorectal cancer detection. Conventional colonoscopy, which is an imperfect gold standard, frequently misses polyps and even large tumors, especially those that are located behind colonic folds. The Aer-O-Scope Colonoscope System, with its omni-directional 360° view capability, was designed to view behind folds and lower the rates of missed polyps. Preclinical animal trials demonstrated that the Aer-O-Scope Colonoscope System was superior to conventional colonoscopy in visualizing polyps¹. This current clinical investigation is intended to compare the visualization of the Aer-O-Scope Colonoscope System to that of conventional colonoscopes commonly used in GI practices today.

1.2 Identification of the Clinical Investigation Plan

Clinical Investigation	Post Market Evaluation of Aer-O-Scope™ Visualization
Reference Number	934CLD
Version of the CIP	Rev. 02
Amendments	n/a
Version/Issue Number and Reference Number	n/a

1.4 Principal Investigator, Coordinating Investigator and Investigation Site(s)

See Appendix 1: Participating Investigators

Clinical Investigational Plan			
Protocol ID	934CLD	Sponsor	GI View Ltd.
Revision	03	Investigational Device	Aer-O-Scope® Colonoscope System

1.5 Overall Synopsis of the Clinical Investigation

Inclusion/Exclusion Criteria	
Inclusion Criteria:
 
 1. Subject is indicated for screening, diagnostic (minor complaints such as rectal bleeding or minor abdominal pain) or surveillance colonoscopy 2. Subject willing to undergo tandem colonoscopies with Aer-O-Scope Colonoscope and a conventional colonoscope (including a single colon preparation bowel cleansing) 3. Subject between the ages of 45 and 75 (patients between the ages of 45 and 50 must have a family history of a first degree relative with onset of colon cancer before the age of 60). 4. Subject is able to understand and willing to sign informed consent form 
Exclusion Criteria:
 
 1. Personal history of colorectal neoplasia including familial adenomatous polyposis or hereditary nonpolyposis, colon cancer (HNPCC). 2. Diagnosis of active (flaring) inflammatory bowel disease (active ulcerative colitis or Crohn's colitis), bowel obstruction, or acute diverticulitis, or known severe diverticulosis, fecal incontinence or any known large-bowel disease that would require a predetermined therapeutic colonoscopy (non-screening, non-diagnostic or non-surveillance cases) 3. Severe gastrointestinal tract-related symptoms, or complaints, suggesting performance of a pre-determined therapeutic colonoscopy (non-screening, non-diagnostic or non-surveillance cases) 4. History of colonic resection 5. Clinically significant cardiovascular or pulmonary disease. 6. Cancer or other life threatening disease or significant chronic condition that puts the subject at risk. 7. Blood-clotting disorders and/or current anticoagulant therapy (Subjects taking up to 100mg aspirin for prophylactic treatment are acceptable for this study) 8. Pregnancy 9. Previous radiation therapy to the abdomen 10. Morbid Obesity (BMI > 40 kg/m²) 11. Drug abuse or alcoholism 12. Subject is bed-ridden and/or unable to adequately communicate 13. Subject is under custodial care 14. Subject has a history of psychiatric disorders which would prevent compliance with study instructions 15. Participation in a clinical study within the previous 30 days
-------------------------------------	---

Clinical Investigational Plan			
Protocol ID	934CLD	Sponsor	GI View Ltd.
Revision	03	Investigational Device	Aer-O-Scope® Colonoscope System

Number of Subjects	
Three hundred and 10 (310):
 
Up to ten (10) training cases per investigator per site) plus eighty (80) study subjects per site (between one hundred (100) and one hundred and ten (110)subjects per site (dependent on the number of investigators including training cases)
 
Each site will have three (3) study cohorts:
 
 ✓ Training cohort (up to the first 10 cases per investigator) Aer-O-Scope colonoscopy followed by conventional colonoscopy (not part of the statistical evaluation for visualization) ✓ Aer-O-Scope colonoscopy followed by conventional colonoscopy ✓ Conventional colonoscopy followed by Aer-O-Scope colonoscopy
Study Duration	One (1) Year
Study Objectives	
1. Primary Objectives:
 
1.1. To measure the adenoma miss rate (AMR) (based on histology) for the Aer-O-Scope colonoscopy as compared to the AMR for conventional colonoscopy in a tandem back-to-back study.
 
The AMR is defined as the percentage of adenomas missed per cohort (either by the Aer-O-Scope colonoscope or a conventional colonoscope) and is measured by the number of missed adenomas (detected in the second pass colonoscopy) divided by the total number of adenomas detected per cohort.
 
See Number of Subjects above for cohort group definitions
 
1.2. To demonstrate the Aer-O-Scope Colonoscope System is safe for the performance of screening, diagnostic (minor cases such as rectal bleeding and/or abdominal pain) and polyp surveillance colonoscopy.
 
2. Secondary Objectives:
 
2.1. To measure the polyp miss rate (PMR) for the Aer-O-Scope colonoscopy as compared to the PMR for conventional colonoscopy in a tandem back-to-back study.
 
The PMR is defined as the percentage of polyps missed per cohort (either by the Aer-O-Scope colonoscope or a conventional colonoscope) and is measured by the number of missed polyps (detected in second pass colonoscopy) divided by the total number of polyps detected per cohort.
 
(See Number of Subjects above for cohort group definitions).
 
2.2. To measure the advanced adenoma (≥10mm with villous histology or with high grade dysplasia based on histology) miss rate (AAMR) for the Aer-O-Scope colonoscopy as compared to the AAMR for conventional colonoscopy in a tandem back-to-back study.
 
The AAMR is defined as the percentage of advanced adenomas missed per cohort (either by the Aer-O-Scope colonoscope or a conventional colonoscope) and is measured by the number of missed advanced adenomas (detected in second pass colonoscopy) divided by the total number of polyps detected per cohort.

Clinical Investigational Plan

Protocol ID	934CLD	Sponsor	GI View Ltd.
Revision	03	Investigational Device	Aer-O-Scope® Colonoscope System

	
It should be noted that the expected number of advanced adenomas will be significantly lower than the number of polyps and the number of adenomas. The evaluation of this objective will most likely not reach statistical significance due to the small expected sample size of advanced adenomas.
 
2.3. To define and document the learning curve for the operation of the Aer-O-Scope Colonoscope System and use of therapeutic access using the Aer-O-Scope Colonoscope System – Using a 5 point Likert Scale (for perceived physician proficiency). The first ten (10) cases will be training for system operation. The first twenty (20) therapeutic interventions per physician will be training for therapeutic access.
 
2.4. Colonoscopy timing for both Aer-O-Scope and conventional colonoscopy will be documented for the following properties:
 
2.4.1. Cecal intubation time (not including therapeutic intervention times)
 
2.4.2. Withdrawal time (not including therapeutic intervention times)
 
2.4.3. Total procedure time (not including therapeutic intervention times)
 
3. Tertiary Objectives:
 
3.1. Timing of therapeutic interventions (see Appendix 3: Therapeutic Accessories Used in This Study) performed with the Aer-O-Scope Colonoscope System will be documented for the purpose of data collection only

Study Endpoints	
1. Primary
 
1.1. Adenoma miss rates (AMR) for each study cohort
 
1.2. No serious adverse events or serious adverse device effects using the Aer-O-Scope Colonoscope System.
 
2. Secondary
 
2.1. Polyp miss rates (PMR) for each study cohort
 
2.2. Advanced adenoma miss rates (AAMR) for each study cohort
 
2.3. Perceived proficiency in Aer-O-Scope operation, mean Likert score between 1-3.
 
2.4. Cecal intubation time (not including therapeutic intervention times)
 
2.5. Withdrawal times (not including therapeutic intervention times)
 
2.6. Total procedure time (not including therapeutic intervention times)
 
3. Tertiary
 
3.1. Therapeutic intervention metrics (time, tool, success rate)

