4 INVESTIGATIONAL DEVICE AND CLINICAL INVESTIGATION RISKS & BENEFITS

Risks	
The risks associated with the Aer-O-Scope Colonoscope are similar to those risks associated with conventional optical colonoscopy. As with all procedures related to colon screening, there are some associated risks. Risks associated with both colonoscopy and the Aer-O-Scope Colonoscope may include but are not limited to the following:
 
 • Lower digestive tract bleeding, • Colon perforation (that may result in inflammation of the peritoneum (peritonitis) or need for emergency medical treatment), • Excessive insufflation of the colon, • Erosion of the colon mucosa, • Sepsis • Venous thrombosis, • Vasovagal events, • Pain, • Ano-rectal Fissures, • Bloating and • Discomfort. 
Anticipated adverse device effects include bloating, flatulence mild in nature, ano-rectal fissures and minor discomfort. These symptoms are all transient and do not pose a potential risk to the subjects’ health.
 
The Aer-O-Scope Colonoscope system has been designed to minimize

--------------	---

Clinical Investigational Plan

Protocol ID	934CLD	Sponsor	GI View Ltd.
Revision	03	Investigational Device	Aer-O-Scope® Colonoscope System

	these adverse effects.

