5 HYPOTHESES OF THE CLINICAL INVESTIGATION

Hypotheses	
1. Primary Hypotheses:
 
1.1. Colonoscopy with the Aer-O-Scope Colonoscope System will have lower AMR than the conventional forward-viewing colonoscopes. The mean adenoma miss rate for conventional colonoscopy as found in the published literature is between 15-40%.
 
The number missed adenomas (NMA) (based on histology) for each of the two cohort groups in back-to-back tandem colonoscopy will be measured.
 
The NMA is defined as the number of adenomas (based on histology) detected during the second pass colonoscopy that were not detected and removed (or tattooed) during the first pass colonoscopy.
 
The AMR will be measured by the NMA divided by the total number of adenomas detected (for each cohort).
 
1.2. Colonoscopy with the Aer-O-Scope Colonoscope System is safe for screening, diagnostic and surveillance colonoscopy.
 
2. Secondary Hypotheses:
 
2.1. Colonoscopy with the Aer-O-Scope Colonoscope System will have a lower PMR than the conventional forward-viewing colonoscopes.
 
The number missed polyps (NMP) for each of the two cohort groups in back-to-back tandem colonoscopy will be measured.
 
The NMP is defined as the number of polyps detected during the second pass colonoscopy that were not detected and removed (or tattooed) during the first pass colonoscopy.
 
The PMR will be measured by the NMP divided by the total number of adenomas detected (for each cohort).
 
2.2. Colonoscopy with the Aer-O-Scope Colonoscope System will have lower AAMR than the conventional forward-viewing colonoscopes.
 
The number missed advanced adenomas (NMAA) (based on histology) for each of the two cohort groups in back-to-back tandem colonoscopy will be measured.
 
The NMAA is defined as the number of advanced adenomas (based on histology) detected during the second pass colonoscopy that were not detected and removed (or tattooed) during the first pass colonoscopy.
 
The AAMR will be measured by the NMAA divided by the total number of adenomas detected (for each cohort). Because approximately only 6% of all adenomas are considered advanced adenomas, the evaluation of this objective will most likely not

-------------------	--

Clinical Investigational Plan			
Protocol ID	934CLD	Sponsor	GI View Ltd.
Revision	03	Investigational Device	Aer-O-Scope® Colonoscope System

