Any subject withdrawn as a result of physician discretion due to concomitant medical issues will be withdrawn prior to the actual colonoscopic procedures. Patients with a large polyp (>20mm) removed during the first pass with a conventional colonoscope will be withdrawn. Patients who receive treatment during the first pass with clips (no other option available) will be withdrawn. Coagulation therapy should be performed either with Argon Plasma Coagulation (APC) or another cautery tool or contact thermal device as per clinical protocol. For the purpose of this clinical investigation, clips should not be used unless there is no alternative. Patients treated with clips *prior to their final pass colonoscopy*, will be withdrawn from the investigation. Physicians may also withdraw any patient due to medical causes if deemed appropriate, including patients that have undergone at least one (1) procedure.

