6.4 Procedures

Procedures	
Subjects indicated for screening, diagnostic (for minor complaints such as rectal bleeding or minor abdominal pain) or polyp surveillance colonoscopy will meet with the physician or clinical coordinator prior to the procedure for a standard pre-procedure evaluation. Following a preliminary evaluation of eligibility, the patient will be informed of the clinical study and offered the opportunity to participate if he/she is an acceptable candidate. Should the subject agree to join the study, they will be provided a copy of the patient informed consent form and provided ample time to review the form. The point of enrollment will be upon signing the patient informed consent form. Subjects who sign the consent form but do not undergo any procedure will be recorded as screen

-------------------	---

Clinical Investigational Plan			
Protocol ID	934CLD	Sponsor	GI View Ltd.
Revision	03	Investigational Device	Aer-O-Scope® Colonoscope System

	
failures on a separate log, and removed from the enrollment roster.
 
The duration of this multi-national study is expected to be twelve (12) months, three (3) months per site. Each enrolled subject will participate for up to seven (7) days which will include the day of the informed consent signature, the bowel preparation and the day of procedures (Aer-O-Scope Colonoscopy and colonoscopy) with a 24-48 hour follow-up period.
 
Up to 200 subjects will be enrolled in the USA and up to 110 subjects will be enrolled in Israel with a total of up to 310 Subjects overall.

--	--

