7 STATISTICAL CONSIDERATIONS

Measurements	The pass criteria for the study objectives are rejecting the Null hypotheses as presented below.
Primary Hypothesis:	Colonoscopy with the Aer-O-Scope Colonoscope System will have lower AMR than the conventional forward-viewing colonoscopes.
Statistical Analysis Assumptions:	
 The Adenomas rate within the sample will be 50% (see Appendix 4: Bibliography). The adenoma rate in the sample, for patients with Adenomas, will be 200% (average of 2 adenomas per person). (see Appendix 4: Bibliography) The differences in AMR between the two groups will be 15% (see Appendix 4: Bibliography) The expected AMR of the two groups will be 0.10 vs 0.25 (see Appendix 4: Bibliography) The drop-out rate will be 10%.
Statistical Analysis Plan: Hypotheses testing based calculations	
 For testing the hypothesis that the Aer-O-Scope Colonoscope System will have lower AMR and PMR than the conventional forward-viewing colonoscopies we will perform the Z-tests for comparing two proportions. The tests will be two-sided with significant level of 5%. To demonstrate the physicians proficiency in operation of (including therapeutic interventions) and visualization with the Aer-O-Scope Colonoscope descriptive statistics will be performed using the Likert Scale questionnaire. A mean score between one (1) and three (3) will denote proficiency.
Sample Size Calculation:	The sample size calculation based on the independence AMR between the two groups. A total of 240 patients are needed to compare the AMR between the groups using Z-test for two proportions comparisons. This number enables a 10% dropout, and does not include 70 patients (20-30 training subjects per site (sub-investigator dependent) for learning qualification. This sample size based on a significant level of 5% and a power of 80% to prove a difference in AMR between the groups.

Clinical Investigational Plan			
Protocol ID	934CLD	Sponsor	GI View Ltd.
Revision	03	Investigational Device	Aer-O-Scope® Colonoscope System

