16 EARLY TERMINATION OR SUSPENSION OF THE CLINICAL INVESTIGATION

Suspension or Premature Termination	
Grounds for suspension or premature termination of the clinical investigation include but are not limited to:
 
Non compliance of the investigational site personnel to the CIP and or investigational procedures
 
Severe Adverse Events that demonstrate danger to the patient population
 
Unethical performance on the part of any of the investigators
 
Device Adverse Effects that demonstrate danger to the patient population or severe flaw in investigational device design
 
Failed audit of investigation with serious flaws to study design,

--	--

Clinical Investigational Plan			
Protocol ID	934CLD	Sponsor	GI View Ltd.
Revision	03	Investigational Device	Aer-O-Scope® Colonoscope System

	
performance or outcomes
 
Business/Financial issues that cannot be resolved
 
Other unforeseen events that give the PI/Sponsor reasonable doubts to the safety and/or performance of the system which will be referred to the Data Safety Monitoring Committee for review prior to determination of suspension or termination.

Blinding/Masking Technique	This clinical investigation does not include any blinding or masking.
Follow-Up	Patients will be followed up 24-48 hours post procedure via telephone by the clinical coordinator at each site. Patients who undergo therapeutic interventions will only be terminated from the study upon receiving the histology results.

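### Primary safety endpoint 1.2 is a zero-event criterion with no safety null, acceptable SAE rate, confidence interval or analysis set, so the plan does not say what zero events, or one event, would establish

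*Combined protocol and SAP*

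**What the plan says.** Section 1.5 lists two primary objectives. The second is "To demonstrate the Aer-O-Scope Colonoscope System is safe for the performance of screening, diagnostic" and surveillance examinations. Section 5 repeats it as primary hypothesis 1.2: "Colonoscopy with the Aer-O-Scope Colonoscope System is safe for screening, diagnostic and surveillance colonoscopy". The matching primary endpoint in section 1.5 is "No serious adverse events or serious adverse device effects using the Aer-O-Scope Colonoscope System".

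Section 7 sets the success rule: "The pass criteria for the study objectives are rejecting the Null hypotheses as presented below". What follows there is the adenoma miss rate (AMR) hypothesis, Z-tests for AMR and polyp miss rate, descriptive Likert statistics and a sample size for AMR. Safety does not appear.

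Other safety provisions are qualitative:
- Section 5 says serious and unexpected events will be evaluated.
- Section 14 defines event types and has a safety board review all events.
- Section 16 lists grounds for termination.

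On risk, section 4 says: "The risks associated with the Aer-O-Scope Colonoscope are similar to those risks associated with conventional optical colonoscopy". On numbers, sections 6.2 and 6.3 expect 310 scanners and 310 subjects, and section 6.4 puts it as "with a total of up to 310 Subjects overall". On follow-up, section 16 says: "Patients will be followed up 24-48 hours post procedure via telephone by the clinical coordinator at each site". Subjects who have an intervention stay in the study until histology is available. Section 6.3 adds that subjects removed for an adverse event are followed until it resolves.

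**The concern.** The objective and hypothesis are worded as a demonstration, but the endpoint is an observed count with no inferential statement attached. Two readings are possible. Under the section 7 pass rule, objective 1.2 has no null to reject and so no route to a pass. Under the endpoint alone, a trial with no recorded SAE would be reported as showing the device to be safe, with no statement of which rates remain compatible with the data. The documents do not say which reading applies.

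The criterion is also fragile in the other direction. A single countable SAE misses a primary endpoint. Section 4 expects risks similar to conventional colonoscopy and lists perforation and sepsis among them, so the plan itself does not anticipate a true rate of zero. With no stated rate, there is nothing against which to judge that one event.

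Two counting questions add to this. Training cases are left out of the visualization analysis only (sections 1.5 and 2), so they can count for safety, but no safety set is named. In addition, both scopes are used back to back by the same operator (section 6.1), and the endpoint ties events to use of the Aer-O-Scope without saying how an SAE is attributed to one pass.

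**Working it through.** **Plan's own figure.** There is none for safety. The only sample size, 240, is for AMR and enters here only as a possible denominator.

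**Inputs.** Exposed subjects: n = 310 (sections 6.2, 6.3 and 6.4), or 240 if the 70 training subjects of section 7 were not counted (310 − 70 = 240). The documents give no SAE rate, acceptable or expected, so the true rates in step 4 are assumptions shown as a range.

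**1. What zero events exclude.** The exact upper limit for 0 of n is 1 − 0.025^(1/n) for a two-sided 95% interval and 1 − 0.05^(1/n) for a one-sided limit.

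| n | Two-sided 95% | One-sided 95% |
|---|---|---|
| 310 | 1.18% | 0.96% |
| 240 | 1.53% | 1.24% |

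**2. Subjects needed to exclude 1% with zero events.** Two-sided: ln(0.025)/ln(0.99), rounded up, is 368. One-sided: ln(0.05)/ln(0.99), rounded up, is 299. At 310 subjects the choice of sidedness alone decides whether 1% is excluded, and the plan states no choice for safety.

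**3. What one event would mean.** The exact (Clopper-Pearson) two-sided 95% interval for 1 of 310 is 0.01% to 1.78%. For 0 of 310 it is 0% to 1.18%. The intervals overlap over most of their length, yet one result meets the endpoint and the other misses it.

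**4. How often at least one event would occur.** P(at least one) = 1 − (1 − p)^310.

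| Assumed true rate p | P(no event) | P(at least one) |
|---|---|---|
| 0.1% | 73.3% | 27% |
| 0.3% | 39.4% | 61% |
| 0.5% | 21.1% | 79% |

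A device with a true rate of 0.5% would meet the endpoint about one time in five, and a device at 0.1% would miss it about one time in four.

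**5. Which SAEs count.** Section 14 defines an adverse event irrespective of its relation to the device and includes comparator and procedural events. Endpoint 1.2 lists SAEs separately from serious adverse device effects. Together these indicate that unrelated SAEs count. Attribution between two passes in one session remains unsettled.

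**The case against.** This is a post-market visualization study sized for AMR. Zero observed events is the strictest observed criterion available, a safety board reviews every event, and section 16 allows termination on safety grounds. All of that is true. None of it supplies a rate, an interval or an analysis set, and the plan lists safety as a primary objective to be demonstrated.

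A reader might infer several stronger things that the documents do not support:

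- *That zero events would fail to demonstrate safety.* Zero of 310 is informative: it excludes rates above about 1%. No acceptable rate is given, so the documents cannot show that this bound is insufficient. They show only that nothing says whether it is enough.
- *That it is open whether unrelated SAEs count.* The section 14 definition and the separate listing in the endpoint largely settle that they do. Only attribution between the two scopes is left open.
- *That far fewer than 310 will be exposed.* Some subjects may never receive the device, because "Patients with a large polyp (>20mm) removed during the first pass with a conventional colonoscope will be withdrawn". But section 6.1 replaces subjects who cannot undergo tandem colonoscopy through poor preparation or another medical determination. Half of randomized subjects also start with the Aer-O-Scope, so some who drop out will already have been exposed. A specific lower figure cannot be derived.

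Rules on who judges relatedness may also lie in the regulations that section 14 cites or in the separate monitoring plan, neither of which can be seen here.

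**Conclusion.** The point stands. A primary conclusion rests on a zero-event rule, and the plan's own pass rule has no safety null to act on. With 310 exposed, zero events would bound the SAE rate at 1.18% (two-sided; 0.96% one-sided). If only 240 counted, the bounds would be 1.53% and 1.24%. Whether any of these is adequate is unstated. One event would miss the endpoint on data barely distinguishable from zero events, and under the assumed rates of 0.1% to 0.5% that would happen in 27% to 79% of trials.

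The bounds depend on the number actually exposed and cover only the follow-up each subject receives. The probabilities rest on assumed rates and on independence between subjects. AMR conduct and analysis are unaffected.

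**What to change.** Replace the zero-event criterion with the proportion of all Aer-O-Scope-exposed subjects who have any SAE, with an exact 95% confidence interval. Include training cases and exposed subjects later withdrawn or replaced. Report the proportion with device-related SAEs beside it, and say in advance how an SAE is attributed when both scopes were used.

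Reword objective and hypothesis 1.2 as estimating the SAE rate. State the bound for the number actually exposed and the follow-up it covers: the 24-48 hour call, to histology after an intervention, and to resolution for subjects removed for an adverse event.

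If a pass/fail claim is kept, the sponsor should state and justify in section 7 a maximum acceptable rate, and say whether a one- or two-sided upper limit is compared with it. A maximum below 1.18% (two-sided) or 0.96% (one-sided) could not be met with 310 exposed even with no events.

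**Cost.** Wording changes to the endpoint, objective, hypothesis and section 7, plus one simple analysis. Estimation needs no extra patients or procedures. The case report form is not in the documents, so whether it already records pass and relatedness for each SAE cannot be seen. The downside is that the simple yes/no safety claim is lost or becomes harder to meet. Relatedness is judged unblinded, which is why the all-SAE proportion should come first.
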